5.8 Rescue Treatment

Rescue intervention (e.g., anti-VEGF, focal/grid macular laser photocoagulation, IVT steroids) may be administered due to worsening DME (i.e., attributable to worsening DME and not another cause) if either of the following occurs and, where possible, after consultation with the Medical Monitor:

- During Treatment Phase
 - Best corrected visual acuity (BCVA) deteriorates 3 lines (15 letters) or more from baseline
 - Central Subfield Thickness (CST) worsening of >100 µm from baseline
- During Follow up Phase (i.e., after Week 16)
 - BCVA deteriorates 3 lines (15 letters) or more from highest BCVA during treatment phase or baseline
 - CST worsening of >100 µm from lowest CST during treatment phase or baseline.

Subjects who receive a rescue intervention in the study eye will be discontinued from further study participation. The Week 24/ED evaluations should be collected prior to study discontinuation and prior to administration of the rescue medication. Details regarding the medications used as rescue treatment must be entered as concomitant medications for the respective study subject.

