3.1 General Study Design

This is a phase 2a, randomized, double-masked, sham-controlled, 3-arm study to evaluate the efficacy, safety, and tolerability of KVD001 Injection as monotherapy in adult subjects with ciDME who have had prior anti-VEGF treatment. Approximately 123 eligible subjects will be randomized into the study.

Subjects will undergo screening for fulfilling the inclusion and exclusion criteria in order to be eligible for this study. Eligible subjects will be stratified based on visual acuity and CST, and then randomly

assigned in a 1:1:1 ratio into the 3 groups described below. Stratified randomization will be performed centrally by visual acuity and CST at Day 1.

- KVD001 6 µg by IVT injection;
- KVD001 3 µg by IVT injection;
- Sham procedure.

Rescue intervention (e.g., anti-VEGF, focal/grid macular laser photocoagulation, IVT steroids) may be administered due to worsening DME (i.e., attributable to worsening DME and not another cause) if either of the following occurs and, where possible, after consultation with the Medical Monitor:

- During Treatment Phase
 - BCVA deteriorates 3 lines (15 letters) or more from baseline
 - CST worsening of >100 µm from baseline
- During Follow up Phase (i.e., after week 16)
 - BCVA deteriorates 3 lines (15 letters) or more from highest BCVA during treatment phase or baseline
 - CST worsening of >100 µm from lowest CST during treatment phase or baseline.

Subjects who receive a rescue intervention in the study eye will be discontinued from further study participation. The Week 24/Early Discontinuation (ED) evaluations should be collected prior to study discontinuation and prior to administration of the rescue medication. Details regarding the medications used as rescue treatment must be entered as concomitant medications for the respective study subject.

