7.3 Safety Set

[figure not shown]
The Safety Set (SAF) will include all randomized subjects who received at least one dose of study treatment. Subjects will be included in the analysis according to the treatment received.

8. General Statistical Considerations

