12.2 Treatment Exposure

Treatment exposure will be measured by time-on-study, time from first injection to last injection, and time to last exposure to study treatment for the analysis of on-treatment AEs (time from first injection plus additional at-risk period following the last injection (the minimum of 28 days and time from last injection to last study visit)).

Time on study is defined as

$$\text{Time on Study (Days)} = [\text{Date of Last Visit} - \text{Date of Visit 2 (Day 1)}] + 1.$$

Time from first injection to last injection is defined as

$$\text{Time from First to Last Injection (Days)} = (\text{Date of Last Injection} - \text{Date of First Injection}) + 1.$$

Time to last exposure to study treatment for the analysis of on-treatment AEs is defined as

$$\text{Time Exposed (Days)} = (\text{Date of Last Injection} - \text{Date of First Injection}) + \text{ADT},$$

where ADT is the additional time exposed after the last injection and is evaluated as

$$ADT = \text{Minimum (28, Date of Last Visit – Date of Last Injection) + 1.}$$

Time on study, time from first injection to last injection, and time exposed for on-treatment adverse event analysis for each subject exposed to study drug will be summarized with continuous descriptive statistics (n, mean, SD, median, IQR, minimum, maximum) for each treatment group, using the SAF population. A subject listing of treatment exposure will also be produced.

[figure not shown]
13. Efficacy Analyses

[Redacted content]

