13.3 Secondary Analyses

The secondary endpoints are the following:

- Change from baseline in CST as measured by SD-OCT
- Proportion of eyes with a ≥ 2 step improvement from baseline in DRSS score
- Change from baseline in BCVA letter count as measured by ETDRS
- Proportion of SEs with ≥ 5 , ≥ 10 , and ≥ 15 BCVA letter gain from baseline and the proportion of SEs with ≥ 5 , ≥ 10 , and ≥ 15 BCVA letter loss from baseline.

Change from baseline in BCVA letter count as measured by ETDRS in the study eye and change from baseline in CST in the study eye as measured by the central image reading center (CIRC) using SD-OCT will be analyzed using the same method described for the primary efficacy analysis. Note that change from baseline in CST will be in favor of KVD001 if the treatment difference is < 0 .

The difference in proportion of SEs with improvement of 2 or more steps on the ETDRS DRSS score between each KVD001 injection dose and the sham and between the KVD001 Injection doses will be summarized by visit using discrete summary statistics, including 95% Clopper-Pearson CIs for each treatment group. The difference in proportions between each KVD001 Injection dose and the sham and between the KVD001 Injection doses will be analyzed using a Pearson's chi-squared test. 95% Clopper-

Pearson CIs for the differences in proportions will also be calculated. Fisher's exact tests and exact CIs will be employed in cases of expected counts <5.

The proportion of SEs with ≥ 5 , ≥ 10 and ≥ 15 BCVA letter change (gain and loss) between baseline and each post-baseline visit will be analyzed using the same method described for the proportion of SEs with improvement of 2 or more steps on the ETDRS DRSS score. Additionally, as an exploratory endpoint, the proportion of SEs with any BCVA letter loss between baseline and each post-baseline visit will be summarized similarly. Note that the categorizations of ≥ 5 , ≥ 10 and ≥ 15 BCVA letter change (gain and loss) or any BCVA letter loss are not mutually exclusive.

14. Safety Analyses

All safety data analyses will be performed on the safety population and displayed in subject data listings and summarized in tables. No statistical inferential testing will be performed for safety variables.

Safety endpoints include AEs, manifest refraction/BCVA, slip lamp biomicroscopy, dilated ophthalmoscopy, intraocular pressure (IOP), SD-OCT, EDTRS DRSS, physical exam findings, laboratory test results, and vital signs.

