- Number of subjects with TEAEs leading to death; and
- Number of subjects with TEAEs by maximum severity.

Overall summaries of AEs will be presented for the following classes of events:

- All AEs (ocular & non-ocular)
- Ocular events for each eye (study eye and fellow eye)
- Non-Ocular events

Frequencies and percentages of subjects with TEAEs, serious TEAEs, TEAEs leading to study drug discontinuation, and treatment-related TEAEs will be provided by treatment group by SOC and PT.

Furthermore, summaries will be given of subjects with TEAEs:

- by SOC, PT, and maximum severity;
- by SOC, PT, and strongest relationship;
- by SOC and PT for SAEs;
- by SOC and PT for TEAEs related to study drug; and
- by SOC, PT, and time of onset (i.e., Day 1 to Week 4 [Days 1-28], > Week 4 to Week 8 [Days 29-56], > Week 8 to Week 12 [Days 57-84], > Week 12 to Week 16 [Days 85-112], > Week 16 [> Day 112]).

Separate analyses will be performed for ocular specific AEs, and all AEs (including systemic).

Summaries of preferred terms (without regard to SOC) will be presented for TEAEs and the most frequent TEAEs (occurring in $\geq 5\%$ of patients treated with KVD001 6 μg or KVD001 3 μg).

Post-treatment AEs, defined as AEs that started or worsened more than 28 days after last injection, will also be summarized.

Subject listings of all AEs including verbatim text will be provided as well as listings of deaths, SAEs, and AEs causing premature discontinuation of study drug.

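### AE tables give each treated subject equal weight although rescue-driven exit shortens observation, and the time at risk derived in SAP 12.2 is used in no AE table

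*SAP*

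**What the plan says.** - **Metric.** SAP 14.1 gives subject frequencies and percentages by arm: "Frequencies and percentages of subjects with TEAEs, serious TEAEs, TEAEs leading to study drug discontinuation, and treatment-related TEAEs will be provided by treatment group". Its overall summaries also count events.
- **Population.** SAP 14 states "All safety data analyses will be performed on the safety population". SAP 7.3 defines that set: "The Safety Set (SAF) will include all randomized subjects who received at least one dose of study treatment". The listed AE tables, 14.3.1.1.1 to 14.3.1.7.2, all name the SAF.
- **Inference.** SAP 14: "No statistical inferential testing will be performed for safety variables".
- **Exit.** SAP 3.1: "Subjects who receive a rescue intervention in the study eye will be discontinued from further study participation". The triggers are loss of visual acuity or a rise in CST. Protocol 5.8 adds: "The Week 24/ED evaluations should be collected prior to study discontinuation and prior to administration of the rescue medication".
- **Time at risk.** SAP 12.2 derives "time to last exposure to study treatment for the analysis of on-treatment AEs" and cuts it off at the last study visit. Its only stated uses are a descriptive exposure summary (Table 14.1.7.2) and an exposure listing (16.2.5.2).
- **Later events.** SAP 14.1: "Post-treatment AEs, defined as AEs that started or worsened more than 28 days after last injection, will also be summarized". TEAEs are also tabulated in onset bands, the last of which begins after Day 112. Neither summary states a denominator for the period.

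**The concern.** Rescue depends on how the eye is doing, so if the drug works or harms, length of observation can depend on treatment. A percentage of subjects ignores that. If more sham subjects are rescued early, sham has less time in which to show AEs and KVD001 looks less safe than it is. If KVD001 subjects leave earlier, some of its AEs go unseen. Safety and tolerability is the secondary objective and no safety tests are planned, so readers will compare the percentages directly.

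The SAP already derives the quantity needed and labels it for AE analysis, then leaves it out of that analysis. Elsewhere it does correct a denominator for rescue: in SAP 12.1, a visit at which rescue is given is not counted among planned injections.

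**Working it through.** The documents give no rescue, exit or AE rate, so there is no stated figure to reproduce. The check starts from the plan's own formula; every rate after step 1 is an assumption.

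**1. Time exposed (SAP 12.2), with visits 28 days apart (Protocol 3.1).** Time exposed = (last injection − first injection) + min(28, last visit − last injection) + 1.
- Four injections, followed to Week 16 or later: 84 + 28 + 1 = 113 days.
- Rescued instead of injected at Week 4: 0 + 28 + 1 = 29 days (26% of 113).
- At Week 8: 28 + 28 + 1 = 57 days (50%).
- At Week 12: 56 + 28 + 1 = 85 days (75%).

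Rescue at Week 16 or later costs no time in the TEAE window.

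**2. Effect on percentages with the same true hazard in both arms.** Assume a 40% AE risk over 112 days, constant hazard, and exits uniform over Days 28 to 84.
- Hazard = −ln(0.6)/112 = 0.00456 per day.
- Risk observed in those who exit = 1 − (0.6^0.25 − 0.6^0.75)/(56 × 0.00456) = 22.3%.
- Crude percentage at exit fraction r = (1 − r) × 40% + r × 22.3%.
- Gap, KVD001 minus sham = (r sham − r KVD001) × 17.7 points.

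| Exit, sham vs KVD001 | Sham | KVD001 | False gap |
|---|---|---|---|
| 10% vs 5% | 38.2% | 39.1% | +0.9 |
| 30% vs 10% | 34.7% | 38.2% | +3.5 |
| 40% vs 10% | 32.9% | 38.2% | +5.3 |
| 30% vs 30% | 34.7% | 34.7% | 0 |
| 10% vs 30% | 38.2% | 34.7% | −3.5 |

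**3. Other assumptions.** Exits are now spread evenly over Weeks 4, 8 and 12, using the step 1 times.
- 30% AE risk: +0.7 (10% vs 5%), +2.1 (20% vs 5%), +3.4 (30% vs 5%), and +5.3 if the 30% vs 5% all leave at Week 4.
- 30% vs 5% exit: +1.2 at 10% AE risk and +5.3 at 50%.
- The harshest combination tried (50% risk, 40% vs 10%, all at Week 4) gives +10.1.

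**4. Which rate removes the gap.** Take the 30% vs 10% case of step 2, with a month of 30.44 days.
- Mean observation: 0.7 × 112 + 0.3 × 56 = 95.2 days on sham; 0.9 × 112 + 0.1 × 56 = 106.4 on KVD001.
- Subjects with an event over uncensored time: 0.347/95.2 × 3044 = 11.1 and 0.382/106.4 × 3044 = 10.9 per 100 subject-months.
- With time censored at first onset, both arms return the hazard: 0.00456 × 3044 = 13.9.

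First-event rates therefore need time censored at first onset, which SAP 12.2 does not derive.

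**5. Period tables, on planned days.**
- Post-treatment: exit at Week 4, 8, 12 or 16 comes 28 days after the last injection, so none of that subject's follow-up lies beyond 28 days. If the full Safety Set were the denominator and 30% had no such follow-up, a 20% rate among those followed would print as 0.7 × 20% = 14%.
- Onset bands: by SAP Table 1 the last injection is planned for Day 84, so the TEAE window closes on Day 112. A dated TEAE can fall in the final band only if the last injection was later than planned.

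**The case against.** Subject percentages beside exposure and disposition tables are an ordinary description for a short Phase 2a trial. Several points in the plan's favour stand.

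- **Rescue ends AE collection** is something a reader might infer, but no section says so. Protocol 4.3.1 follows AEs that caused withdrawal, and Protocol 6.2.1.8 follows open AEs to resolution or Week 24 and SAEs beyond. Those rules concern events already recorded. New AEs are picked up at visits and calls, and SAP 12.2 itself stops risk time at the last visit. Shortened observation of new AEs is a reasonable inference, no more.
- **The period tables divide by the full Safety Set** is also tempting. The table list names the SAF as the analysis set; it does not give the n for each period. The denominator is unstated, not wrong.
- **Partly recoverable.** Event counts are planned in the overall summaries, and n × mean time exposed gives total subject-time by arm, so crude overall event rates can be worked out. SAP 9 also shows rescue before Week 16 and reasons for discontinuation by arm. Rates by SOC and PT and first-event rates are not recoverable this way.
- **Size.** Rescue is optional, needs a loss of at least 15 letters or a CST rise above 100 µm, and subjects must be judged able to defer treatment for 6 months. At 41 per arm, 3.5 points is about 1.4 subjects. The standard error of the difference is √[(0.347 × 0.653 + 0.382 × 0.618)/41] = 10.6 points, about three times the bias.

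**Conclusion.** The point holds as a gap in the AE summaries. Counts and subject percentages take no account of outcome-related differences in observation time, and a variable derived for on-treatment AE analysis is not used in it. That rests on the text, apart from the inference about new AEs after exit.

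The size rests on assumed exit rates and a constant, equal hazard: about 0 to 5 points in most scenarios, more only when exit is very unequal and early or AEs are very common. The documents do not support saying that the tables will favour either arm, because the direction follows whichever arm leaves earlier. With no safety testing planned, no formal conclusion turns on this. It is a modest possible distortion of a descriptive comparison, cheap to remove.

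**What to change.** Amend SAP 14.1 and keep the crude percentages.

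1. By arm, for overall, serious, treatment-related and study-eye TEAEs, add two rates: (a) number of events per 100 subject-months of SAP 12.2 time exposed; (b) subjects with a first event per 100 subject-months, with time exposed censored at that subject's first onset of the event class.
2. In the onset-band tables (14.3.1.5.1 and 14.3.1.5.2), use and show as denominator the number still under observation, and still within the TEAE window, at the start of each band.
3. In Table 14.3.1.2.9, use and show the number followed more than 28 days after the last injection.

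The cost is minor programming: rate (a) uses an existing variable, while rate (b) needs a censored time for each event class. No trial procedure changes. Both rates assume a roughly constant hazard, which is doubtful for AEs of the injection procedure, so label them supportive and descriptive.

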3 OVERALL DESIGN AND PLAN OF THE STUDY

3.1 Overview

This is a phase 2a, randomized, double-masked, sham-controlled, 3-arm study to evaluate the efficacy, safety, and tolerability of KVD001 Injection as monotherapy in adult subjects with ciDME who have had prior anti-VEGF treatment. Approximately 123 eligible subjects will be randomized into the study.

The maximum duration of the study for each randomized subject will be up to 28 weeks (including up to 4 weeks for screening, 12 weeks treatment period, and 12 weeks follow-up).

The study will be conducted on an out-patient basis.

The study schedule of events will be as follows:

Screening Phase: The screening period will be up to 4 weeks prior to study Day 1. All subjects will sign an Informed Consent Form (ICF) prior to any study related procedures being performed. Subjects will be 18 years of age or older, at the time of screening, and will have a diagnosis of ciDME with prior anti-VEGF treatment.

Treatment Phase: On the day of first study drug administration (Day 1), the subject's eligibility will be reconfirmed and baseline assessments will be performed. Eligible subjects will be randomized 1:1:1 to receive KVD001 Injection (6 µg or 3 µg KVD001) or a sham procedure during a 12-week, double-masked treatment period (a total of 4 doses given at approximately monthly intervals).

Subjects will visit the study clinic on Day 1 and Weeks 4, 8, and 12 during the Treatment Phase for study drug administration or sham procedure, safety, and ophthalmic assessments (see [Table 2](#)). The subject will remain in the clinic after study drug administration or sham procedure until all post-dose procedures and observations have been completed and the Investigator confirms that the subject may be discharged. Investigators should schedule visits at Week 4, 8, and 12 to provide 28 days between visits. The visit window for these visits is -3 days to +7 days.

Approximately twenty-four (24) hours after each study drug administration or sham procedure on Day 1 and Weeks 4, 8, and 12, subjects will be contacted by telephone to evaluate any reported AEs and changes in concomitant medications. In the event of any reported ocular or systemic AEs that are considered by the Investigator to be a possible cause for concern, the subjects will return to the clinic for assessment as soon as possible.

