5.2 Administration

KVD001 Injection or sham procedure will be administered to the study eye on Day 1 and Weeks 4, 8, and 12 during the Treatment Phase. At each scheduled visit, the date and time of study medication administration will be recorded in the eCRF.

The injecting physician cannot be the Investigator as they should remain masked throughout the study. In order to avoid breaking the mask, real and sham injections will be performed by study personnel who are not masked and not otherwise involved in the study (note that post-injection IOP evaluations must be performed by study personnel who are unmasked). For sham injections, the subjects will be prepared exactly as for a real injection (i.e., including but not limited to: insertion of lid speculum, application of povidone-iodine and subconjunctival injection of an anesthetic) following which an empty syringe with no needle will be pressed against the eye to mimic the pressure of an injection.

Please refer to the Pharmacy Manual for detailed instructions on administration.

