8.6.1 Adverse Events

AEs will be coded using the MedDRA dictionary. Frequencies and percentages of subjects with treatment-emergent adverse events (TEAEs), serious TEAEs, and TEAEs causing premature discontinuation will be provided by treatment group. An AE is treatment emergent if it 1) occurs after the first dose of randomized study treatment or 2) if it is present prior to receipt of randomized study treatment but worsens in severity or increases in frequency after the first dose of randomized study treatment. Furthermore, frequencies will be given of subjects with TEAEs by system organ class and preferred term; by system organ class, preferred term and maximal severity; by system organ

class, preferred term and strongest relationship; by system organ class and preferred term for SAEs; and by system organ class, preferred term, and day of onset. Separate analyses will be performed for ocular specific and all AEs (including systemic). AEs will be classified by System Organ Class (SOC) and preferred term in the MedDRA coding dictionary. AEs will be tabulated both as the total events (regardless of relationship to treatment) and as drug-related events. The number of subjects with one or more events versus no events will be calculated for each treatment.

Subject listings of all AEs will be provided as well as listings of deaths, SAEs, and AEs leading to discontinuation.

The following summaries will be provided:

- Relationship between AE SOC and verbatim text;
- On-treatment AEs: number and percentage of subjects reporting each AE, each AE leading to withdrawal, each SAE, each drug-related SAE, each fatal AE, and most frequent by treatment;
- Post-treatment AEs: number and percentage of subjects reporting each AE;
- Listing of all AEs;
- Summary of Most Frequent AEs.

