8.5 Adjustments for Multiplicity

Adjustments for multiple treatment comparisons, analysis time points, and/or endpoints will not be made for this exploratory study.

9. Disposition of Subjects

Subject disposition will be presented in terms of the numbers and percentages of subjects who were screened, screen failures, randomized, randomized but not treated, completed the Week 16 visit (without rescue medication/procedure prior to the visit), completed the study, discontinued from the study, and rescued prior to the Week 16 visit. Subjects who are not discontinued from the study will be considered study completers. Disposition will be summarized by treatment group and for all enrolled subjects.

The number and percentage of subjects completing the study or who prematurely discontinued from the study and the reasons for study discontinuation will be summarized by treatment group for all randomized subjects. The reasons for study discontinuation prior to completion include: adverse event, use of rescue medication, subject compliance, withdrawal of consent, lost to follow-up, sponsor termination of study, positive pregnancy test, and other. A subject listing will be provided that includes the date of completion or discontinuation and reason for premature study discontinuation.

[figure not shown]
The number and percentage of subjects with protocol deviations will be summarized by treatment group for all randomized subjects. A subject listing will be provided that includes the start/end date of the deviation, the deviation description, deviation code, (informed consent, inclusion/exclusion and randomization, test article/study drug administration at site, improper protocol procedures at site, site failure to report serious adverse event (SAE)/AE, visit out of window, subject's use of prohibited concomitant medication, subject's failure to follow instructions, or other reasons) and the classification of whether the deviation was judged to be major or minor.

In addition, listings for all enrolled subjects will be provided that include informed consent date, randomization date/time, randomization number, inclusion and exclusion criteria violations, unmasking information, and exclusions from the FAS and PPS populations.

10. Demographic and Other Baseline Variables

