14.1 Adverse Events

An AE is defined as any untoward medical occurrence associated with the use of an investigational product (IP) in humans, whether or not considered IP-related. AEs starting on or after the date of first exposure to study drug and up to 28 days after last injection will be considered treatment-emergent adverse events (TEAEs). AEs with unknown onset dates will be counted as a TEAE. All AEs will be assigned a severity grade of mild, moderate, or severe. Their relationship to study drug will be classified as suspected or not suspected. TEAEs with a missing relationship to study treatment will assume greatest relationship to study treatment (suspected). Only suspected TEAEs are considered as treatment-related. TEAEs with missing severity grades will be categorized as severe for tabulation of TEAEs by severity. The expectedness of an AE will be classified as unexpected, expected or not applicable (not applicable for AEs unrelated to IP). Documentation of AEs will include onset date, location (right eye [OD], left eye [OS], both eyes [OU], not ocular), severity, action(s) taken, relationship to study drug, expectedness, outcome, resolution date, and seriousness. All AEs will be coded using MedDRA classifications with reference to SOCs and PTs (MedDRA version 20.1).

An AE is considered serious if, in the view of either the investigator or sponsor, it results in any of the following outcomes:

- Death
- A life-threatening AE
- Inpatient hospitalization or prolongation of existing hospitalization

- A persistent or significant incapacity or substantial disruption of the ability to conduct normal life functions
- A congenital anomaly/birth defect
- Medically Significant.

Important medical events that may not result in death, be life-threatening, or require hospitalization may be considered serious when, based upon appropriate medical judgment, they may jeopardize the subject and may require medical or surgical intervention to prevent one of the outcomes listed above.

Overall summaries of AEs will be presented showing:

- Number of AEs and number of subjects with any AEs;
- Number of TEAEs and number of subjects with any TEAEs;
- Number of treatment-related TEAEs and number of subjects with any treatment-related TEAEs;
- Number of SAEs and number of subjects with any SAEs;
- Number of treatment-emergent SAEs and number of subjects with any treatment-emergent SAEs;
- Number of subjects with TEAEs leading to premature discontinuation;

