14.3.1.2.2	Ocular Treatment-Emergent Adverse Events by Eye, System Organ Class, and Preferred Term	SAF Population
14.3.1.2.3	Serious Adverse Events by System Organ Class and Preferred Term	SAF Population
14.3.1.2.4	Ocular Serious Adverse Events by Eye, System Organ Class, and Preferred Term	SAF Population

[figure not shown]
14.3.1.2.5	Treatment-Emergent Adverse Events Leading to Study Drug Discontinuation by System Organ Class and Preferred Term	SAF Population
14.3.1.2.6	Ocular Treatment-Emergent Adverse Events Leading to Study Drug Discontinuation by Eye, System Organ Class, and Preferred Term	SAF Population
14.3.1.2.7	Treatment-Related Treatment-Emergent Adverse Events by System Organ Class and Preferred Term	SAF Population
14.3.1.2.8	Ocular Treatment-Related Treatment-Emergent Adverse Events by Eye, System Organ Class, and Preferred Term	SAF Population
14.3.1.2.9	Post-Treatment Adverse Events by System Organ Class and Preferred Term	SAF Population
14.3.1.3.1	Treatment-Emergent Adverse Events by System Organ Class, Preferred Term, and Maximum Severity	SAF Population
14.3.1.3.2	Ocular Treatment-Emergent Adverse Events by Eye, System Organ Class, Preferred Term, and Maximum Severity	SAF Population
14.3.1.4.1	Treatment-Emergent Adverse Events by System Organ Class, Preferred Term, and Relationship to Study Drug	SAF Population
14.3.1.4.2	Ocular Treatment-Emergent Adverse Events by Eye, System Organ Class, Preferred Term, and Relationship to Study Drug	SAF Population
14.3.1.5.1	Treatment-Emergent Adverse Events by System Organ Class, Preferred Term, and Time of Onset	SAF Population
14.3.1.5.2	Ocular Treatment-Emergent Adverse Events by Eye, System Organ Class, Preferred Term, and Time of Onset	SAF Population
14.3.1.6.1	Treatment-Emergent Adverse Events by Preferred Term	SAF Population
14.3.1.6.2	Ocular Treatment-Emergent Adverse Events by Eye and Preferred Term	SAF Population
14.3.1.7.1	Most Frequent ($\geq 5\%$ of KVD001-Treated Subjects) Treatment-Emergent Adverse Events by Preferred Term	SAF Population
14.3.1.7.2	Most Frequent ($\geq 5\%$ of KVD001-Treated Subjects) Ocular Treatment-Emergent Adverse Events by Eye and Preferred Term	SAF Population
14.3.4.1	Best Corrected Visual Acuity (Letter Count) by Visit and Eye	SAF Population
14.3.4.2	Central Subfield Thickness (μm) by Visit and Eye	SAF Population
14.3.4.3	Early Treatment Diabetic Retinopathy Study Diabetic Retinopathy Severity Score in the Study Eye by Visit	SAF Population

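### No by-term table identifies the AEs that made a subject leave the study after the last dose at Week 12

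*SAP*

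**What the plan says.** - **Dosing and follow-up.** Protocol 5.2: study treatment "will be administered to the study eye on Day 1 and Weeks 4, 8, and 12 during the Treatment Phase". Protocol 3.1 gives "12 weeks treatment period, and 12 weeks follow-up".
- **Protocol on discontinuation.** Section 4.3 treats stopping further dosing and withdrawing from the study as two different actions. Section 8.6.1 plans frequencies by treatment group of TEAEs that caused premature discontinuation. Among its on-treatment summaries it asks for the number and percentage of subjects with "each AE leading to withdrawal". It also plans a listing of AEs that led to discontinuation. None of these is limited to study drug, and the protocol's TEAE definition has no end date.
- **SAP by-term output.** Section 14.1: frequencies of "TEAEs leading to study drug discontinuation, and treatment-related TEAEs will be provided by treatment group by SOC and PT". The table list in Section 19 agrees. Table 14.3.1.2.5 is titled "Treatment-Emergent Adverse Events Leading to Study Drug Discontinuation by System Organ Class and Preferred Term", and Table 14.3.1.2.6 is its ocular counterpart.
- **SAP TEAE window.** Section 14.1: AEs from first exposure "up to 28 days after last injection will be considered treatment-emergent adverse events (TEAEs").
- **SAP overall summary.** Section 14.1 also counts subjects with TEAEs that led to premature discontinuation. This line has no study-drug limit and shows no terms.
- **SAP listing.** The text of 14.1 promises a listing of "AEs causing premature discontinuation of study drug". The title of Listing 16.2.7.3 has no study-drug limit.
- **Disposition.** SAP Section 9: "The reasons for study discontinuation prior to completion include: adverse event, use of rescue medication, subject compliance", among others. No AE term is attached.

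**The concern.** The SAP states that its methods supersede those in the protocol, so its criterion decides what is produced. After the fourth dose there is no study drug left to discontinue. A subject who completes the course and then leaves because of an AE therefore fails the condition for both by-term discontinuation tables, however long the TEAE window runs. Section 16 lists the changes from the protocol's analyses and does not mention this one.

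Safety and tolerability are the secondary objective. Which AEs made subjects leave, by arm, is a basic tolerability result, and an ocular effect that builds up over repeated injections could show itself after the last one. As the tables stand, a reader would have to reconstruct those exits from listings.

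The SAP is also inconsistent with itself. The overall line, the by-term text, the listing text and the listing title do not share one criterion, so a programmer cannot tell which condition applies.

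**Working it through.** The plan states no figure on this point, so there is none to reproduce. The check is arithmetic on planned days and a comparison of the outputs.

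**Inputs.** Last planned dose: Week 12 = Day 84. Planned end: Week 24 = Day 168 (both SAP Table 1). TEAE window: 28 days after the last injection (SAP 14.1). Week 12 visit window: -3 to +7 days (Protocol 3.1).

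**Days after the last dose**
- Follow-up after dosing: 168 - 84 = 84 days, and 84/168 = 50% of the planned period.
- End of TEAE window: 84 + 28 = Day 112. With the visit window it lies between 81 + 28 = Day 109 and 91 + 28 = Day 119.
- Inside the TEAE window: Days 85 to 112 = 28 days (28/84 = 33% of follow-up; 28/168 = 17% of the planned period).
- Post-treatment: Days 113 to 168 = 56 days (56/84 = 67% of follow-up; 56/168 = 33% of the planned period).

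**Where the exit appears.** Take a subject who has had all four doses and leaves the study because of an AE.

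| SAP output | Onset Days 85-112 | Onset after Day 112 |
|---|---|---|
| All TEAEs by SOC and PT (14.3.1.2.1) | yes, not marked as cause of exit | no |
| Post-treatment AEs by SOC and PT (14.3.1.2.9) | no | yes, not marked as cause of exit |
| By-term discontinuation (14.3.1.2.5, 14.3.1.2.6) | no | no |
| Overall count of TEAEs leading to premature discontinuation | yes | no |
| Listing of AEs causing discontinuation, by 14.1 text | no | no |
| Same listing, by title of 16.2.7.3 | yes | yes |
| All-AE listing (16.2.7.1) | yes | yes |
| Disposition | reason only, no term | reason only, no term |

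**Reading the table**
- Every day to Week 24 has a by-term AE table. No day after a complete course has a by-term table that shows the AE as the reason for leaving.
- In the first column, the overall count and the by-term discontinuation tables can differ, with no term shown for the difference. The same can happen if a TEAE began during dosing but made the subject leave only after the fourth dose.
- In the second column, the overall count also loses the exit, because it is limited to TEAEs.

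**The case against.** The strongest reply is that little is lost. The AE itself is always tabulated by term. A subject leaving around Week 14 (Day 98) for an AE of recent onset is in Table 14.3.1.2.1, in the Days 85 to 112 column of the time-of-onset table, in the overall discontinuation count, and under the title of Listing 16.2.7.3. In a study of about 123 subjects, a listing can show each such case. This stands, and it limits the point to a missing label.

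The protocol also asks for less than one might assume. Its by-term request for AEs leading to withdrawal sits under on-treatment AEs. The next item, on post-treatment AEs, asks only for each AE, and Table 14.3.1.2.9 supplies that. The protocol does not define on-treatment, but SAP 12.2 extends exposure for on-treatment AEs by at most 28 days after the last injection. On that reading, the departure from the protocol's by-term request covers Days 85 to 112, or 17% of the planned period. This stands too. A by-term row for later exits goes beyond that request. It is proposed for completeness, although the protocol's open-ended TEAE definition does bring later exits into its overall frequency of discontinuations.

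Three stronger readings are tempting, and the documents do not support them:
- **The AE disappears from all by-term output, or from the listings.** Tables 14.3.1.2.1 and 14.3.1.2.9 and Listings 16.2.7.1 and 16.2.7.3 contradict this.
- **Half of the study is lost against the protocol.** The 50% is the share of planned time after the last dose. It is not the size of the departure from Protocol 8.6.1.
- **AEs are hidden when a subject leaves through rescue.** Separate disposition reasons do not decide which AEs enter an AE table. Rescue is for worsening DME and has its own listings (16.2.1.2, 16.2.4.1.5, 16.2.4.3.6). Counting it as AE withdrawal would mix lack of efficacy with tolerability.

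**Conclusion.** The point holds in a limited form. No by-term table identifies AEs that led to withdrawal from the study after the last dose, this is narrower than Protocol 8.6.1, and SAP Section 16 does not declare it. For onset on Days 85 to 112 (28 of 168 planned days), the overall count and the by-term tables can disagree. For onset after about Day 112 (56 planned days), the overall count omits the exit as well.

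This rests on the planned visit days, on a complete four-dose course, and on reading the overall line as it is worded, without a study-drug limit. The boundary moves between Day 109 and Day 119 with the Week 12 visit window. The documents give no expected rate of withdrawal for AEs, so the number of subjects affected cannot be estimated. The consequence is an incomplete and internally inconsistent descriptive safety output. No efficacy result is affected.

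**What to change.** 1. In SAP 14.1 and Tables 14.3.1.2.5 and 14.3.1.2.6, change the criterion to AEs that led either to discontinuation of study drug or to withdrawal from the study. Show the two in separate rows, and show post-treatment AEs that led to withdrawal in a row of their own.
2. Remove the study-drug limit from the listing text in 14.1 so that it matches the title of Listing 16.2.7.3.
3. Record in Section 16 any departure from Protocol 8.6.1 that remains.

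With the first change, the by-term tables agree with the overall TEAE count and with the protocol's request.

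The cost is minor programming. SAP 14.1 includes actions taken among the AE data, and Section 9 includes the reason for leaving. The documents do not show a field that links a given AE to study withdrawal, so this should be confirmed on the eCRF; Listing 16.2.7.3, as titled, needs the same link. The count of withdrawals for AEs may look slightly less favourable.
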